Appendix 20. MDAAT	
Appendix 21. MMT-8	
Appendix 22. TIS using Core Set Measures in DM	189
Appendix 23. Muscle Damage Index, MDI	190
Appendix 24. CTFG Guidelines ³⁴ Regarding Contraception for Germany	191
Appendix 25. Contraceptive and Barrier Guidance	192
Appendix 25.1. Male Participant Reproductive Inclusion Criteria	192
Appendix 25.2. Female Participant Reproductive Inclusion Criteria	192
Appendix 25.3. Women of Childbearing Potential	193
Appendix 25.4. Contraception Methods	194

SCHEDULE OF ACTIVITIES (STAGE 1 AND STAGE 2)

This SoA pertains to the DM population with focus on skin disease. Stage 1 enrolled participants to 600 mg or placebo. Stage 2 enrolled participants to 600 mg, 150 mg or placebo.

The schedule of activities table provides an overview of the protocol visits and procedures. Refer to the STUDY PROCEDURES and ASSESSMENTS sections of the protocol for detailed information on each procedure and assessment required for compliance with the protocol.

The investigator may schedule visits (unplanned visits) in addition to those listed on the schedule of activities table, in order to conduct evaluations or assessments required to protect the well-being of the participant.

Protocol Activity	Screenin g	T	reatment								
Visit identifier (Study Visit)	1	2	3	4	5	6	7	8	9	10	Participant withdrawal or Early Termination ^a
Study Day/Week	Days -35 to -1	Baseline Day 1	Week 1 Day 8	Week 4 Day 29	Week 8 Day 57	Week 12 Day 85	Week 16 Day 113	Week 20 Day 141	Week 24 Day 169	Week 28 Day 197 EOS	N/A
Visit Window	None	None				±	3 days				
Screening Assessments											
Informed consent	Х										
Inclusion/exclusion criteria	Х	Х									
Demography	Х										
Medical history	Х	Xb									
DM History	Х										
Prior DM medication history	Х	Xb									
Prior Non DM medications	Х	Xb									
Clinical reported outcomes											
CDASI Score	Х	Х	Х	Х	Х	Х	Х	Х	Х		Х
PHQ-8 assessment ^c	Х										
CCI											
Physician global assessment, (PhGA) ^e		X	Х	X	Х	X	Х	Х	Х	Х	X
Patient Reported Outcomes											
5D Pruritus Scale ^f		X	Х	Х	Х	Х	Х	Х	Х	Х	X
SF36 V2 Acute ^f		Х	Х	Х		Х				Х	Х
DLQI ^f		Х	Х	Х		Х				Х	Х

Protocol Activity	y Screenin Treatment Follow-up					Follow-up					Follow-up			
Visit identifier (Study Visit)	1	2	3	4	5	6	7	8	9	10	Participant withdrawal or Early Termination ^a			
Study Day/Week	Days -35 to -1	Baseline Day 1	Week 1 Day 8	Week 4 Day 29	Week 8 Day 57	Week 12 Day 85	Week 16 Day 113	Week 20 Day 141	Week 24 Day 169	Week 28 Day 197 EOS	N/A			

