Study Day/Week	Days -35 to -1	Baseline Day 1	Week 1 Day 8	Week 4 Day 29	Week 8 Day 57	Week 12 Day 85	Week 16 Day 113	Week 20 Day 141	Week 24 ^y Day 169	Week 28 Day 197	Week 32 Day 225	Week 36 Day 253	Week 40 Day 281 EOS	N/A
Visit Window	None	None		•	•			•	±3 days	•			•	
Screening Assessments														
Informed consent	Х													
Inclusion/exclusion criteria	Х	Х												
Demography	Х													
Medical history	Х	Xb												
DM History	Х													
Prior DM medication history	Х	Xb												
Prior Non DM medications	Х	Xb												
Clinical Reported Outcomes		·							•					-
CDASI Score	X	Х	Х	Х	Х	Х	Х	Х	Х	Х	Х	Х	Х	Х
PHQ-8 assessment ^c	Х													
CCI														
Physician Global Assessment, (PhGA, VAS) ^e		X	X	X	Х	X	X	Х	X	X	Х	Х	X	X
Patient Reported Outcomes ^f														
PtGA		Х	Х	Х	Х	Х	Х	X	Х	Х	Х		Х	Х

Protocol Activity	Screening	Treatment Period									Follow-u			
Visit identifier (Study Visit)	1	2	3	4	5	6	7	8	9 ^y	10	11	12	13 ^r	Participant
														withdrawal or
														Early
														Termination ^a
Study Day/Week	Days	Baseline	Week	Week 4	Week	Week	Week	Week 20	Week 24 ^y	Week	Week 32	Week	Week	N/A
	-35 to -1	Day 1	1	Day 29	8	12	16 D	Day 141	Day 169	28 Day	Day 225	36 D	40 D	
			Day 8		Day 57	Day 95	Day 112			197		Day 253	Day 291	
					57	03	115					233	FOS	
Visit Window	None	None			1		l		±3 days	1			105	
HAQ-DI		Х	Х	Х	Х	Х	Х	Х	X	Х	Х		Х	Х
5-D Pruritus Scale		Х	Х	Х	Х	Х	Х	Х	Х	Х	Х		Х	Х
CCI														
SF-36 v2 Acute		Х	Х	Х	_	Х	Х		X			1	Х	X
DLQI		Х	Х	Х		Х	Х		Х	Х			Х	Х
EQ-5D-5L & EQ-VAS		Х	Х	Х			Х			Х			Х	
Medical Assessments														
Vital Signs (BP, HR, Pulse, Respirations	Х	Х	Х	Х	Х	Х	Х	Х	Х	Х	Х	Х	Х	Х
and temperature) ^g														
Weight ^h	Х	Х				Х			Х				Х	Х
Height ^h	Х								Х				Х	
Complete physical examination ⁱ	Х					Х			Х				Х	Х
Targeted physical examination ¹		Х	Х	Х	Х		Х	Х		Х	Х	Х		
ECG	Х	Х		Х	Х	Х	Х	Х	X				Х	Х
Chest X-Ray ^j	Х													
Skin Punch Biopsies ^k		Х				Х			Х					
Contraception check	Х	Х	Х	Х	Х	Х	Х	Х	Х	X	Х	Х	Х	Х
Laboratory Assessments		1		1	1	1					1			
Safety Labs/Urine	Х	Х		Х	Х	Х	Х	Х	X ^z	Х	Х	Х	Х	Х
Urine β-hCG		Х	Х	Х	Х	Х	Х	Х	Х	Х	Х	Х	Х	Х
(conducted at site) ^m														
Serum β-hCG ^m	Х													
Follicle stimulating hormone FSH	Х													
(WONCBP only)														
Viral surveillance (eg, CMV, VZV, EBV, -	Х	Х		Х	Х		Х	Х			Х		Х	Х
HHV6, HSV-1/2) ⁿ														
HIV, HBsAg, HBcAb, HCVAb ^o	Х													
Quantiferon [®] TB Gold test ^p	Х									L		 _		_
CCI	1													

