- w. Once the infusion has completed, all participants will be monitored for an additional 60 minutes post investigational treatment administration.
- x. All participants who are on IVIG concomitantly will have a pre-dose blood sample collected. See Section 7.15.
- y. All participants who complete the treatment period in this study up through and including (Visit 9, Week 24), will have the opportunity to continue treatment in the open label extension C0251008 protocol. Participants whom have completed the treatment period and have not had any significant protocol deviations, or safety events will be eligible. Participants will also have the opportunity to continue into the follow up period and complete the C0251002 study instead of enrolling into open label extension C0251008.
- z. All participants continuing to the open label extension C0251008 study should use the DAY 1 C0251008 Lab kit. Please see lab manual for specific instructions.
SCHEDULE OF ACTIVITIES (STAGE 3)

This SoA focuses on DM participants with moderate muscle disease. The approximate study duration is 45 weeks including the screening period. Participants enrolling in Stage 3 will not provide any skin or muscle biopsies.

The schedule of activities table provides an overview of the protocol visits and procedures. Refer to the STUDY PROCEDURES and ASSESSMENTS sections of the protocol for detailed information on each procedure and assessment required for compliance with the protocol. The investigator may schedule visits (unplanned visits) in addition to those listed on the schedule of activities table, in order to conduct evaluations or assessments required to protect the well-being of the participant.

Protocol Activity	Screening				Treatm	ent Period					Follow	-up Period		
Visit identifier (Study Visit)	1	2	3	4	5	6	7	8	9 ^y	10	11	12	13	Participant withdrawal or Early Termination ^a
Study Day/Week	Days -35 to -1	Baseline Day 1	Week 1 Day 8	Week 4 Day 29	Week 8 Day 57	Week 12 Day 85	Week 16 Day 113	Week 20 Day 141	Week 24 ^y Day 169	Week 28 Day 197	Week 32 Day 225	Week 36 Day 253	Week 40 Day 281 EOS ^r	N/A
Visit Window	None	None							±3 d	ays				•
Screening Ass	sessments		_										-	
Informed consent	Х													
Inclusion/excl usion criteria	Х	Х												
Demography	Х													
Medical history	X	Xb												
DM History	Х													
Prior DM medication history	Х	Xb												
Prior Non DM	X	Xb												Х
medications			I	L			L						1	1

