9.4. Safety Analysis

The safety analysis population will include all participants who have received at least one dose of study drug or placebo. Safety data will be presented in tabular and/or graphical format and summarized descriptively, where appropriate. All safety endpoints will be listed and summarized in accordance with Pfizer Data Standards. Categorical outcomes (eg, AEs) will be summarized by participant counts and percentage. Continuous outcome (eg, BP, heart rate) will be summarized using N, mean, median, standard deviation. Change from baseline in laboratory data and vital signs will also be summarized according to sponsor Data Standards. Participant listings will be produced for these safety endpoints accordingly.

Safety analyses will be reported for Stage 1, Stage 1 and 2 combined, and Stage 3 as described in Section 2.

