9.4.2. Electrocardiogram

Changes from baseline for the ECG parameters (QT interval, heart rate, corrected QT interval QTc (QTcB and QTcF versions) and QRS interval will be summarized by treatment and time. The Day 1 pre-dose ECG measurements will be used as a participant's baseline. The number (%) of participants with maximum post dose QTc values (QTcB or QTcF) and maximum increases from baseline in the following categories will be tabulated by treatment:

	Borderline (msec)	Prolonged (msec)
Absolute Value	≥ 450 - <480	≥480
Absolute Change	30-<60	≥60

In addition, the number of participants with absolute QTc values \geq 500 msec will be listed.

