2.2. Study Design

Initially, this was a multi-center Phase 2A study planned to be conducted in approximately 30 adult participants with moderate to severe DM. Thirty two participants were randomized in order to collect data from 24 participants who completed the study. Each participant was to take part in the study for a period of approximately 9 months. After the 35 day screening period, participants who were eligible enrolled into the study and were randomized in a blinded manner, 2:1 (Active:Placebo) ratio. Investigational drug or placebo administration took place on Day 1, Week 4, and Week 8 of the study. Participants then entered a 5-month follow-up period.

For Stage 2, with the addition of 1 lower dose 150 mg arm, this study then became a Phase 2, dose-finding double-blind, randomized, placebo-controlled study. Approximately 20 additional participants who meet eligibility criteria will be enrolled and randomly assigned in a blinded manner to receive PF-06823859 600 mg, 150 mg, or placebo dosed every 4 weeks according to a randomization ratio. 5:11:4. Participants will receive study drug, (active or placebo) on Day 1, Week 4, and Week 8 of the study and when treatment is completed all participants will enter a 5-month follow-up period.

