6.7. Safety Summaries and Analyses

The safety will be monitored over the study period that includes treatment and follow-up periods in all stages.

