6.7.1. Adverse Events

It should be recognized that most studies are not designed to reliably demonstrate a causal relationship between the use of a pharmaceutical product and an adverse event or a group of adverse events. Except for select events in unique situations, studies do not employ formal adjudication procedures for the purpose of event classification. As such, safety analysis is generally considered as an exploratory analysis and its purpose is to generate hypotheses for further investigation. Separate AE tables will show the data from (a) Stage 1, (b) Stage 1, Stage 2, and Amended Stage 2, and (c) Stage 3.

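### Pooled AE table (b) gives crude percentages with no stated time window, although observation length differs by stage and 150 mg comes only from Stage 2 onward

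*SAP*

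**What the plan says.** **Tables and measure.** SAP 6.7.1 plans three sets of AE tables: "Separate AE tables will show the data from (a) Stage 1, (b) Stage 1, Stage 2, and Amended Stage 2, and (c) Stage 3". For the measure, Protocol 9.4 states: "Categorical outcomes (eg, AEs) will be summarized by participant counts and percentage". SAP 6.6.3 summarises exposure only as the number of doses.

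**Window.** SAP 6.7 opens with "The safety will be monitored over the study period that includes treatment and follow-up periods in all stages". SAP 9.3.1 ties treatment-emergent events to an effective duration of treatment that is not defined in weeks. SAP Section 3 limits pooled skin-stage analyses to the first 12 weeks, but in a paragraph about efficacy endpoints.

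**Length of observation (Protocol, Schedules of Activities).** Stage 1 and original Stage 2 end at "Week 28 Day 197 EOS" and Amended Stage 2 at "Week 40 Day 281 EOS". Amended Stage 2 participants who complete Week 24 "will have the opportunity to continue treatment in the open label extension C0251008 protocol".

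**Dose by stage.** Stage 1 randomised 32 participants 2:1 to 600 mg or placebo. Stage 2 was to add about 20, with a "randomization ratio. 5:11:4" for 600 mg, 150 mg and placebo (SAP 2.2).

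**ECG.** Protocol 9.4.2 tabulates, by treatment, participants with "maximum post dose QTc values (QTcB or QTcF) and maximum increases from baseline" in set categories. SAP 6.7.4 summarises the ECG categories by treatment and study week.

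**The concern.** A crude percentage counts participants with at least one event, so it rises with the time watched. In table (b) the time watched depends on stage, and stage depends on dose. About 21 of 26 participants on 600 mg and 11 of 15 on placebo come from the 28-week Stage 1, against none of 11 on 150 mg. If table (b) is read by dose over all follow-up, 150 mg could look less safe or safer than 600 mg with no difference in risk.

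Tolerability across the skin stages is a secondary objective, and this is the planned table that sets the doses side by side. The direction of any artefact depends on how many participants followed the amended schedule and how many left at Week 24. A reader therefore cannot correct for it by eye.

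**Working it through.** **The plan's own figure.** The documents state no AE or ECG rate. The only stated figure for the pooled arms is the 90% CI half-length in Protocol 9.1.2, with SD 8. It reproduces with the normal quantile:
- 150 mg vs placebo: 1.645 × 8 × √(1/10 + 1/11) = 5.75 (stated 5.75)
- 600 mg vs placebo: 1.645 × 8 × √(1/21 + 1/11) = 4.90 (stated 4.90)

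**Arm sizes.** Stage 1 gives 32 × 2/3 = 21.3 on 600 mg and 10.7 on placebo. Stage 2 at 5:11:4 of 20 gives 5, 11 and 4. Pooled: 600 mg 26.3, 150 mg 11, placebo 14.7.

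**Unknowns.** Let *f* be the share of Stage 2 participants on the amended schedule and *g* the share of those leaving at Week 24. The documents give neither, so both run from 0 to 1.

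**Model.** One constant hazard applies in all arms. All follow-up is credited to the Day 1 arm. Risk by week *t* is 1 − (1 − 0.20)^(*t*/28):
- 28 weeks: 20.0%
- 40 weeks: 27.3%
- 24 weeks: 17.4%

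Each arm's percentage is the average over its participants. For 600 mg with *f* = 1, *g* = 0: (21.3 × 20.0 + 5 × 27.3)/26.3 = 21.4%.

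| *f* | *g* | Mean weeks, 150 / 600 / placebo | Crude AE %, 150 / 600 / placebo |
|---|---|---|---|
| 0 | any | 28.0 / 28.0 / 28.0 | 20.0 / 20.0 / 20.0 |
| 0.5 | 0 | 34.0 / 29.1 / 29.6 | 23.6 / 20.7 / 21.0 |
| 0.5 | 1 | 26.0 / 27.6 / 27.5 | 18.7 / 19.8 / 19.6 |
| 1 | 0 | 40.0 / 30.3 / 31.3 | 27.3 / 21.4 / 22.0 |
| 1 | 0.75 | 28.0 / 28.0 / 28.0 | 19.9 / 20.0 / 20.0 |
| 1 | 1 | 24.0 / 27.2 / 26.9 | 17.4 / 19.5 / 19.3 |

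The gap between 150 mg and 600 mg runs from 27.3 − 21.4 = +5.9 points to 17.4 − 19.5 = −2.1 points. It almost vanishes at *g* = (40 − 28)/(40 − 24) = 0.75. For an event with 50% risk at 28 weeks the two ends are 62.9 / 52.4 / 53.5% and 44.8 / 49.0 / 48.6%.

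**Common window.** Over 12 weeks the same 20% event gives 1 − 0.8^(12/28) = 9.1% in every arm.

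**ECG, Protocol 9.4.2 maximum only.** Scheduled post-baseline ECGs number 4 in Stage 1 and original Stage 2 (Weeks 4, 8, 12, 28). Amended Stage 2 has 7 (Weeks 4, 8, 12, 16, 20, 24, 40), or 6 if the participant leaves at Week 24. With an assumed independent 5% chance per ECG, the risk is 1 − 0.95^4 = 18.5%, 1 − 0.95^7 = 30.2% or 1 − 0.95^6 = 26.5%. For 150 mg / 600 mg / placebo:
- *f* = 1, *g* = 0: 30.2 / 20.8 / 21.7%
- *f* = 1, *g* = 1: 26.5 / 20.1 / 20.7%
- *f* = 0: 18.5% in each arm

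Limited to Weeks 4, 8 and 12, it is 1 − 0.95^3 = 14.3% in each arm.

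**The case against.** **The whole-study window is not stated.** A reader might infer that the AE percentages certainly run to Week 28, 40 or 24. The documents do not say so: SAP 6.7 speaks of monitoring, and SAP 9.3.1 points to a treatment-emergent window. This stands, and it is why the result is conditional. It does not remove the problem, because the treatment-emergent window has no length. A window tied to the last study infusion would still differ by 12 weeks, since dosing ends at Week 8 in Stage 1 and original Stage 2 and at Week 20 in Amended Stage 2.

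**The problem cannot be separated from the Week 12 switch.** It is tempting to say that it persists at the same size when every event is attributed correctly. The table above does not show that, because it credits all follow-up to the Day 1 arm. In Amended Stage 2, active and placebo change over at Week 12 without washout. Counting by treatment received would move time between columns and alter the size, perhaps also the sign. The SAP gives no attribution rule for AE tables.

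**ECG.** A reader might infer that the SAP's ECG tables are distorted too. They are not: SAP 6.7.4 is by study week, so doses are compared at the same visit. Only the cumulative maximum in Protocol 9.4.2 is exposed. SAP 9.7 also words its categories as maxima, so which table will be produced needs settling.

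**Size and precision.** The SAP calls safety analysis exploratory. The arms are small: one of 11 participants is 9.1 points, and the standard error of a difference near 20% is √(0.16/11 + 0.16/26) = 14 points. The artefact lies well inside the noise. It is nevertheless systematic and cheap to avoid. Stage 1 has its own AE table, but it contains no 150 mg and so does not help that comparison.

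**Conclusion.** The point holds in conditional form. Table (b) has no stated window, person-time rate or post-switch attribution rule, and its stages differ in length of observation in a way tied to dose. AE percentages can therefore differ by dose through observation time; the documents do not show that they will. For an event with 20% risk at 28 weeks, the artefact between 150 mg and 600 mg is about +6 to −2 points, and nil if no one followed the amended schedule.

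This rests on a constant equal hazard, percentages over all follow-up by Day 1 arm, about 20 Stage 2 participants at 5:11:4, and two shares that the documents do not give. It is a worthwhile improvement to the safety reporting and does not invalidate the plan.

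**What to change.** Add a paragraph to SAP 6.7.1 for pooled table (b):

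- Make the by-dose AE comparison on events from Day 1 to the Week 12 visit, before any Week 12 infusion. All skin stages share this period. State how events dated on the day of that visit are handled.
- Report later events separately as exposure-adjusted rates (for example per 100 participant-weeks) by treatment being received. State the attribution rule, including for events after the change from active to placebo, where there is no washout.
- Reconcile Protocol 9.4.2 with SAP 6.7.4 on the QTc categories. Either keep the table by study week, or limit the maximum to the Week 4, 8 and 12 ECGs.

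The cost is one SAP paragraph and one extra table set from data already collected. No planned AE output has to be dropped.

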6.7.2. Laboratory Data

Laboratory data will be listed and summarized by treatment in accordance with the sponsor reporting standards. The laboratory data listing will be listed for all stages and stage will be indicated.

6.7.3. Vital Signs

Systolic blood pressure, diastolic blood pressure and pulse rate will be listed and tabulated by dose group and week with descriptive statistics (N, mean, standard deviation, median, minimum and maximum). Change from baseline (defined as mean pre-dose value collected at Week 0) will also be summarized using the same descriptive statistics by dose group and week in (a) Stage 1, (b) Stage 1, Stage 2, and Amended Stage 2, and (c) Stage 3.

The numbers of subjects with vital sign outcomes within the specified categories (see Section 9.7) will be tabulated by treatment and study week.

6.7.4. Electrocardiogram

The following ECG data will be listed: QT, QTc (Fridericia's), heart rate, QRS duration, PR interval. QTc based on Fridericia's correction will be derived.

Baseline and change from baseline for QT, QTcF, heart rate, QRS, PR will be summarized using descriptive statistics by treatment and study week in (a) Stage 1, (b) Stage 1, Stage 2, and Amended Stage 2, and (c) Stage 3. For QTcF a classification of absolute values and increase from baseline will be used.

The numbers of subjects with ECG outcomes within the specified categories (see Section 9.7) and number of subjects with uncorrected QT values \geq 500 ms will be summarized by treatment and study week.

6.7.7. Physical Examination

All physical exam data will be provided in the listings.

6.7.8. Other Safety Data

Prior medication(s), non-drug treatment(s), medical history, lab data and physical examination will be listed in accordance with the sponsor reporting standards. Any other data that is captured on the study database, will be listed.

7. INTERIM ANALYSES

7.1. Introduction

In Stage 1 of the study, an interim analysis was performed when 32 participants were randomized and completed Visit 6 (Week 12). Additional interim analyses during later stages of the study *may* be conducted depending on the enrollment rate. If an additional interim analysis is done in the future, an internal review committee (IRC) independent from the blinded study team will review efficacy and safety data for business decision planning, if applicable. The results of the interim analysis will not be shared with the study team, participants, or investigators.

It is expected that in addition to the study team, an unblinded team may review the (ie, any data not explicitly stated as primary or secondary endpoint) and exposure data on an ongoing basis. The analyses of the group will not be included into the report described in the current SAP.

